5.13 Primary and Secondary Sustained Clinical Improvements

The rates of primary and secondary sustained clinical improvements are to assess the changes in Rutherford classification from baseline at 1 month, 6 months, 12 months, 24 months, and 60 months.

The primary sustained clinical improvement is defined as an improvement in Rutherford classification of one or more categories as compared to baseline without the need for repeat TLR.

The secondary sustained clinical improvement (i.e. clinical success) is defined as an improvement in Rutherford classification of one or more categories as compared to baseline including those subjects with repeat TLR. The clinical success at 1 month, 6 months, and 12 months are included in the protocol-defined additional assessments.

The clinical deterioration is defined as downgrade in Rutherford classification of one or more categories as compared to baseline.

5.14 Hemodynamic Improvement

The rate of hemodynamic improvement is to assess the changes in ABI from baseline at 1 month, 6 months, and 12 months. The definition of improvement is to observe either the ABI measurement ≥ 0.9 or the change from baseline ≥ 0.1 .

There are two scenarios for hemodynamic improvement shown below.

Subject #1's baseline ABI= 0.95 and 12-month ABI= 1.0. The subject #1 shows 12-month improvement due to 12-month observed ABI= 1.0.

Subject #2's baseline ABI= 0.6 and 12-month ABI= 0.8. The subject is 12-month improvement due to the ABI increase of 0.2 (i.e. 0.8 – 0.6) regardless of 12-month ABI measurement of 0.8 (i.e. <0.1).

Note that the ABI deterioration is defined as observing 0.1 or more in ABI decrease from baseline.

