**Table 25.2-1: Definitions**

Term	Definition
DIAMETER STENOSIS	The maximal narrowing of the target lesion relative to the reference vessel diameter.
DISSECTION- NHLBI GRADE TYPES	Type A- Small radiolucent area within the lumen of the vessel disappearing with the passage of the contrast material. Type B- Appearance of contrast medium parallel to the lumen of the vessel disappearing within a few cardiac cycles. Type C- Dissection protruding outside the lumen of the vessel persisting after passage of the contrast material. Type D- Spiral shaped filling defect with or without delayed run-off of the contrast material in the antegrade flow. Type E- Persistent luminal filling defect with delayed run-off of the contrast material in the distal lumen. Type F- Filling defect accompanied by total vessel occlusion.
DISTAL EMBOLIZATION	Migration of a filling defect, or thrombus, to distally occlude the target vessel or one of its branches.
HEMATOMA	A localized swelling filled with blood resulting from a break in a blood vessel.
HEMODYNAMIC IMPROVEMENT	Improvement of ABI by $\geq 0.1$ or to an ABI $\geq 0.90$ as compared to the pre-procedure value without the need for repeat revascularization.
HEMODYNAMIC SUCCESS	Hemodynamic success is defined as a positive change in Ankle-Brachial Index compared to baseline.
HYPOTENSION	Systolic blood pressure $< 80$ mmHg lasting more than 30 minutes or requiring intervention (e.g. pacing, IABP, intra venous vasopressors to sustain systolic blood pressure). This excludes transient hypotension or vagal reactions, which are self-limited or readily reversible.
INTIMAL FLAP	An extension of the vessel wall into the arterial lumen.
LESION LENGTH	Measured as the distance from the proximal shoulder to the distal shoulder of the lesion, in the view that demonstrates the stenosis in its most elongated projection.
MAJOR ADVERSE EVENTS (MAEs)	Major Adverse Events (MAEs) include all-cause death, target limb unplanned major amputation and/or target lesion revascularization (TLR).

Table 25.2-1: Definitions

Term	Definition
MINIMAL LUMEN DIAMETER	The vessel diameter as measured at the narrowest point of the lesion.

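### The SAP's hemodynamic improvement rate is looser than the protocol's: it drops the no-repeat-revascularization condition, and its ABI ≥ 0.9 branch ignores baseline

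*SAP*

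**What the plan says.** SAP 5.14 presents the hemodynamic improvement rate as a measure of ABI change from baseline at 1, 6 and 12 months. Its rule for improvement is "either the ABI measurement ≥ 0.9 or the change from baseline ≥ 0.1". Two worked cases follow. In the first, "Subject #1's baseline ABI= 0.95 and 12-month ABI= 1.0", and the conclusion is: "The subject #1 shows 12-month improvement due to 12-month observed ABI= 1.0". In the second, ABI goes from 0.6 to 0.8: "The subject is 12-month improvement due to the ABI increase of 0.2". The section ends with a companion definition: "ABI deterioration is defined as observing 0.1 or more in ABI decrease from baseline". It does not mention repeat revascularization.

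Protocol Table 25.2-1 defines hemodynamic improvement as a gain of at least 0.1, or improvement to at least 0.90, "as compared to the pre-procedure value without the need for repeat revascularization".

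Hemodynamic success is a different measure. It means any positive ABI change from baseline. It is the one listed as an additional endpoint in protocol 6.2.2 and in the SAP 5.1 lists for the 30-day and 12-month reports.

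**The concern.** The two documents use one name for two rules, and the SAP's rule is the more favorable. The SAP gives no reason for the difference.

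The two departures work differently. Without the revascularization condition, subjects who needed a second procedure are credited as improved. Without a baseline reference in the 0.9 branch, a subject can be improved without any gain in ABI, or after a loss. Because deterioration is defined separately as a fall of 0.1 or more, the two categories are not mutually exclusive.

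At stake is how a descriptive rate reads at three time points. SAP section 2 says the specified analyses may go to competent authorities and into publications.

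**Working it through.** **Rules.** Let b be baseline ABI and f follow-up ABI.

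- SAP improved: f ≥ 0.9 or f − b ≥ 0.1
- SAP deteriorated: b − f ≥ 0.1
- Crossing rule (one reading of the protocol): f − b ≥ 0.1, or b < 0.9 and f ≥ 0.9; no repeat revascularization
- Any-rise rule (the other reading): f − b ≥ 0.1, or f ≥ 0.9 and f > b; no repeat revascularization

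**The SAP's own cases reproduce.** For 0.95 to 1.0 the change is +0.05, below 0.1, so the subject passes only through the level branch. For 0.6 to 0.8 the change is +0.2, so the subject passes through the change branch.

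**Other pairs under the same rules** (no repeat revascularization):

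| b → f | f − b | SAP improved | SAP deteriorated | Crossing | Any rise |
|---|---|---|---|---|---|
| 0.95 → 1.0 | +0.05 | yes | no | no | yes |
| 0.95 → 0.95 | 0 | yes | no | no | no |
| 1.0 → 0.95 | −0.05 | yes | no | no | no |
| 1.05 → 0.92 | −0.13 | yes | yes | no | no |
| 1.0 → 0.90 | −0.10 | yes | yes | no | no |
| 0.88 → 0.91 | +0.03 | yes | no | yes | yes |
| 0.6 → 0.8 | +0.2 | yes | no | yes | yes |

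If the 0.6 → 0.8 subject had a repeat revascularization, the SAP still says improved and the protocol says not improved.

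**Where the 0.9 branch goes wrong.** An unchanged or lower subject counts as improved only if f ≥ 0.9 and f ≤ b, which needs b ≥ 0.90. Both labels apply only if f ≥ 0.9 and b − f ≥ 0.1, which needs b ≥ 0.9 + 0.1 = 1.0.

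**Can such baselines occur?** Protocol 8.2 and 8.3 select on Rutherford category 2 to 4 and angiography. No criterion limits baseline ABI, and the SAP's first case starts at 0.95.

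**Size of the 0.9-branch effect.** The documents give no ABI distribution, so these inputs are assumptions: normally distributed true ABI, no true change, and measurement SD 0.07 at each visit. The simulation gave:

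| Baseline mean / SD | Measured b ≥ 0.9 | SAP rule | Crossing rule | Excess (points) | Both labels |
|---|---|---|---|---|---|
| 0.60 / 0.15 | 3.5% | 17.9% | 16.3% | 1.6 | 0.15% |
| 0.65 / 0.15 | 6.5% | 19.9% | 16.7% | 3.2 | 0.3% |
| 0.70 / 0.18 | 15% | 26.6% | 17.5% | 9.1 | 1.1% |
| 0.75 / 0.20 | 24% | 33.9% | 17.9% | 16.0 | 2.2% |

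Most of the crossing-rule rate is noise in the change branch: 1 − Φ(0.1 / (0.07 × √2)) = 1 − Φ(1.01) ≈ 15.6%. The protocol's definition has the same branch, so this part is not a SAP error. Only the excess column is.

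Against the any-rise rule the excess is smaller. That rule gives 21.5% in the third scenario and 24.9% in the fourth, so the excess is 26.6 − 21.5 = 5.1 and 33.9 − 24.9 = 9.0 points.

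For scale, 60 subjects are planned for the primary cohort. If all were evaluable, 1.6 to 16 points would be about 0.016 × 60 ≈ 1 to 0.16 × 60 ≈ 10 subjects.

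**Size of the revascularization effect.** This cannot be computed from the documents. It depends on how many subjects have a repeat procedure and then meet the ABI rule.

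**The case against.** **The measure is minor.** Hemodynamic improvement is not the listed endpoint. Hemodynamic success is, and an unchanged or lower ABI cannot count as success. SAP 5.1 makes all additional assessments observational, with no formal tests. This stands and limits the reach of the point. A reader might infer that the listed endpoint, or the study's success criteria, are biased. The documents do not support that.

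**The protocol does not state a baseline below 0.9.** Its text can also be read as reaching 0.90 with some rise over the pre-procedure value. On that reading the SAP's first case (0.95 to 1.0) qualifies. This stands too. That subject did rise, so the case shows that the stated reason ignores baseline; it is not an example of an unchanged or worse subject. Neither reading admits 0.95 to 0.95 or 1.05 to 0.92, and the missing revascularization condition depends on neither.

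**The SAP does use baseline.** Its stated purpose and its 0.1 branch both refer to it. Correct: only the 0.9 branch lacks the reference.

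**High baselines may be rare.** Rutherford 2 to 4 and stenosis of at least 70% make a low ABI likely, and the protocol's definitions link an ABI below 0.9 to disease. That bears on the size of the effect, which is why the range starts near 2 points. It does not remove the effect, since nothing excludes such subjects.

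A reader might also take roughly a quarter to a third falsely improved (26.6% to 33.9%) as the measure of the error. Those totals come from the higher assumed baselines and include the 15.6% of noise that the protocol's rule shares.

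**Conclusion.** The point holds for a descriptive rate. SAP 5.14 omits a condition that the protocol states, and its 0.9 branch, followed as written, classes some unchanged or worse subjects as improved. These are separate faults: the first credits subjects who had a repeat procedure, and the second affects only subjects with baseline ABI of at least 0.90. Overlap with deterioration needs a baseline of at least 1.0.

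Both faults push the rate upward. For the second, the excess is about 2 to 16 percentage points against the crossing rule, given no true change, measurement SD 0.07, and baseline means of 0.60 to 0.75 with SD 0.15 to 0.20. It is smaller against the any-rise rule. It is governed by the share of subjects with baseline of at least 0.90, which the documents do not give. The first fault is unquantified.

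The primary endpoints, alpha, power and hemodynamic success are not affected.

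**What to change.** Amend SAP 5.14 as follows.

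1. Restore the protocol's condition that improvement is counted only without repeat revascularization. State how its timing relative to each ABI measurement is judged, since the protocol does not spell that out.
2. Make the 0.90 branch relative to the pre-procedure value. The minimum is a follow-up of at least 0.90 that is also higher than baseline. Preferably, require reaching 0.90 from a baseline below 0.90, and label this as a clarification because it is not existing protocol text. Under either version, improvement needs a rise and deterioration needs a fall, so the two cannot overlap.
3. Align the first worked case with the version chosen: 0.95 to 1.0 stays improved under the any-rise rule and becomes not improved under the crossing rule. In the second case, the parenthetical comparison of 0.8 with 0.1 looks like a slip for 0.9 and can be corrected at the same time.

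The cost is SAP wording and a small programming change. SAP 5.16 provides for amendment before the primary endpoint analysis. The reported rate may be slightly lower.

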5.15 Analyses Software

All statistical analyses will be performed and validated by the independent CRO (e.g. IQVIA in Bangalore) using the Statistical Analysis Software (SAS), version 9.2 or later (Copyright © 2002-2010 by SAS Institute Inc., Cary, North Carolina 27513, USA. All rights reserved). BSC will review statistical reports.

5.16 Changes to Planned Analyses

Any changes to the planned statistical analyses made prior to performing the primary endpoint analysis will be documented in an amended Statistical Analysis Plan approved prior to performing the analysis. Changes from the planned statistical methods after performing the analysis will be documented in the clinical study report along with a reason for the deviation.

6 VALIDATION

All clinical data reports generated per this plan will be validated per 90702587, Global WI: Clinical Data Reporting Validation. Statistical analyses and validation will be done by an independent CRO.

7 PROGRAMMING CONSIDERATIONS

All statistical programming tasks will be performed by the independent CRO.

7.1 Derivation for Primary Patency

The primary patency is based on PSVR measurement derived from the core laboratory data provided by Vascular Ultrasound Core Lab (i.e. VASCORE), clinically driven TLR determined by CEC form, and bypass surgery determined in the text field by AE form.

A subject's 12-month primary patency is derived as patent (i.e. "YES") only if:

- VASCORE form: a subject's 12-month DUS assessment is done and PSVR ≤ 2.4 ; and
- CEC form: no clinically-driven TLR prior to 12-month DUS visit. Note that if there is one clinically-driven TLR and the event date is later than ($>$) 12-month DUS visit, the subject's primary patency will remain "YES"; and
- AE form: no bypass surgery is identified prior to 12-month DUS visit. Note that if there is one surgery and the surgery date is later than ($>$) 12-month DUS visit, the subject's primary patency will remain "YES".

7.2 Derivation for Assisted Primary Patency

The assisted primary patency is based on PSVR measurement derived from VASCORE form only. A subject's 12-month assisted primary patency is derived as "YES" only if the subject's 12-month DUS visit is within 12-month window and PSVR ≤ 2.4 .

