**Table 4.2-1: Major Adverse Events at 30 Days and 6 Months**

	30 Days (n=172)	6 Months (n=162)
MAE	2 (1.1%)	31 (19%)
TVR	0 (0%)	4 (2.5%)
Death*		
Sudden Cardiac Arrest (probable)	0 (0%)	1 (0.6%)
Amputation	2 (1.1%)	2 (1.2%)
TLR	0 (0%)	25 (15%)
Non-Q wave MI	0 (0%)	1 (0.6%)

At the 6-month follow-up, 31 subjects had at least 1 MAE. The freedom from serious adverse device effects (SADEs) and TLR at 6 months post-procedure, was 85% with a 95% lower confidence interval of 78%.

Success in crossing and debulking the target lesion was achieved in 99% (208/210) of the cases. Thirty-three percent of the cases were atherectomy procedures alone, while in 59% of the lesions, adjunctive low-pressure angioplasty was also employed. Stenting was indicated in 7% of the subjects. Mean diameter stenosis was reduced from  $79.4\% \pm 17.7\%$  at baseline to  $35.0\% \pm 16.1\%$  after atherectomy. After adjunctive therapy, the diameter stenosis was further reduced to  $21.4\% \pm 10.5\%$ . Interventional success, defined as residual stenosis  $\leq 30\%$  by visual estimation, was achieved in 209/210 (99%) lesions.

Clinical success was achieved in 68% (91/133) at 6 months and 70% (75/107) at 12 months, based on improvement in Rutherford classification. Hemodynamic success was achieved in 52% (63/121) subjects at 6 months and in 52% (51/98) at 12 months.

Primary and secondary duplex-documented patency rates at 12 months were 61.8% (76/123 lesions) and 81.3% (100/123 lesions), respectively. Clinically driven TLR rates were 15% (25/172) at 6 months and 26% (42/162) at 12 months, while TVR rates (including TLR) were 17% (29/172) and 30% (49/162), at 6 and 12 months respectively.

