### **10. Study Methods**

#### **10.1. *Data Collection***

The data collection schedule is shown in Table 10.1-1. Please note that the time window for 30-day follow-up is +/- 7 days, for 6 or 12 months follow-up is +/- 30 days.

The table below is an overview of all the procedures or tests required per protocol. If an examination/test is required, it is marked with "X"; if it is optional but recommended, it is marked with "O".

Table 10.1-1: Data Collection Schedule

Procedure/Assessment	Screening (≤ 30 days prior to index procedure)	Enrollment	Index Procedure	Post- procedure/ Pre-hospital Discharge	Follow-up Visit g		
					30-day (± 7 Days)	6-month (± 30 Days)	12-month (± 30 Days)
In-person Visit	X	X	X	X	X	X	X
Informed Consent process, including informed consent signature date	X						
Demographics (including date of birth, gender, and race and ethnicity)	X						
Physical Assessment	X						
Medical History (including, concomitant diseases, concomitant medication and medical treatments)	X	X d	X d	X d	X d	X d	X d
Routine Laboratory (including serum creatinine, CBC with platelet count tests, and pregnancy test within 7 days of index procedure for potential child-bearing women)a	X						
DUSb	O			O		X	X
ABI	X				X	X	X
Rutherford Categories Assessment	X c				X	X	X
Angiographic assessmentb		X e	X f				
Procedural assessment (including PTA/stenting)			X f				
Adverse Events and Device Deficiency Assessment			X	X	X	X	X

X = required; O = optional but recommended

DUS = Duplex Ultrasound; ABI = Ankle Brachial Index; PTA = Percutaneous Transluminal Angioplasty

a: Excluded from the study if serum creatinine > 2.0mg/dL (176.8umol/L), or platelet count < 80,000/mm^3, or > 600,000 mm^3, or positive pregnancy test (pregnancy test is required within 7 days prior to index procedure for potential child-bearing women)

b: Angiographic and DUS recordings will be sent to the respective core labs for analysis. Follow-up angiograms and DUS will not be required for those subjects who underwent by-pass surgery of the target lesion during the 12-month follow-up time frame.

c: Inclusion criterion: Rutherford category 2 - 4

d: Antiplatelet medication assessments

e: Adhere to Angiographic Inclusion criteria.

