**25.2. Definitions**

**Table 25.2-1: Definitions**

Term	Definition
AMPUTATION	
 
Major Amputation: amputation of the lower limb at the ankle level or above; and can be further specified as below-the-knee and above-the-knee amputations, as well as planned and unplanned amputations.
 
Minor Amputation: amputation of the lower limb below the ankle level, i.e. forefoot or toes.
 

ANKLE-BRACHIAL INDEX (ABI)	
The ratio between the systolic pressure measured at the ankle and the systolic pressure measured in the arm as follows:
 
 
Ankle: The systolic pressure will be measured in the target limb at the arteria dorsalis pedis and/or the arteria tibialis posterior. If both pressures are measured, the highest pressures will be used for the ABI calculation.
 
Brachial: The systolic pressure will be measured in both arms, and the highest of both pressures will be used for the ABI calculation.
 
 
An ABI <0.9 indicates the presence of peripheral arterial disease in symptomatic patients as well as in asymptomatic patients. In addition, an ABI <0.9 reflects the presence of generalized asymptomatic or symptomatic atherosclerotic disease, and its associated increased cardiovascular risk.

ARRHYTHMIA	Any variation from the normal rhythm of the heartbeat, including but not limited to, sinus arrhythmia, premature beats, heart block, ventricular or atrial fibrillation, ventricular tachycardia, or atrial flutter.
ASSISTED PRIMARY PATENCY	Percentage (%) of lesions without clinically-driven TLR and those with clinically-driven TLR (not due to complete occlusion or by-pass) that reach endpoint without restenosis.
BLEEDING COMPLICATION	Includes, but is not limited to, intracranial hemorrhage, GI bleeding, hematoma, bleeding at percutaneous catheterization site, and/or retroperitoneal bleeding. Bleeding that requires surgery qualifies as an SAE.
CALCIFICATION	Readily apparent densities seen within the artery wall and site of lesion as an x-ray-absorbing mass.

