5.8 Duplex Ultrasound

Duplex Ultrasound (DUS) assessments will be performed at 6 months (182 ± 30 days) and 12 months (365 ± 30 days) post-index procedure. Only records obtained during the clinical visit window will be selected for analysis unless the Biostatistics personnel are informed otherwise. In the case where multiple examinations are performed during the visit window, the best interpretable record will be selected. Measurements from DUS assessments that occur after a TLR will not be excluded from selection, but rather, endpoint definitions will appropriately account for the presence or absence of a prior TLR. Therefore a prior TLR may suggest a primary patency failure regardless of DUS result(s).

In the determination of $>50\%$ stenosis, a $PSVR > 2.4$ is used for the primary assessment. However a $PSVR > 2.0$ (e.g. alternative definition of vessel patency in SuperNOVA; BMS) and/or $PSVR > 2.5$ (e.g. definition of vessel patency in MAJESTIC; DES) and/or other clinical recommendation may be used in post-hoc analyses for publication purpose

The primary patency (binary rates) will be calculated based on the subjects who have adequate follow-up and/or have DUS assessments. The denominator will be based on number of subjects who reach the protocol-defined lower window and/or have events. The numerator will be based on number of subjects who finish the scheduled assessments (i.e. success or failure) within the protocol-defined upper window.

Follow-up Visit	Protocol Defined Lower ¹ Window for Assessment	Protocol Defined Upper Window for Assessment
6 Months	152	212
12 Months	335	395

¹Days for adequate follow-up

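### SAP 7.2 derives assisted primary patency from PSVR alone, so a lesion re-opened after complete occlusion can count as patent although the protocol's definition excludes it

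*SAP*

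**What the plan says.** The protocol's definitions table (Table 25.2-1) counts two groups as assisted-primary patent: lesions with no clinically-driven TLR, and "those with clinically-driven TLR (not due to complete occlusion or by-pass) that reach endpoint without restenosis". A lesion whose TLR was for complete occlusion, or was a bypass, is left out.

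SAP 7.2 gives the programming rule: "The assisted primary patency is based on PSVR measurement derived from VASCORE form only". A subject is YES at 12 months when the "12-month DUS visit is within 12-month window and PSVR" is at most 2.4. The rule does not mention TLR, occlusion or bypass.

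Three other places bear on this:

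- SAP 7.1 derives primary patency from the ultrasound core-lab form, the CEC form (clinically-driven TLR) and the AE form. Its third condition is "AE form: no bypass surgery is identified prior to 12-month DUS visit".
- SAP 5.8 states that "Measurements from DUS assessments that occur after a TLR will not be excluded from selection", because "endpoint definitions will appropriately account for the presence or absence of a prior TLR".
- Footnote b to the data collection schedule (Protocol 10.1) says: "Follow-up angiograms and DUS will not be required for those subjects who underwent by-pass surgery of the target lesion".

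**The concern.** The two documents attach the same name to different measures. Under the protocol, some re-interventions are failures that later patency cannot repair. Under SAP 7.2, a later scan with an acceptable velocity ratio makes the subject a success whatever happened before it. The subjects affected are those with the most serious loss of patency, and every disagreement runs in the device's favour.

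At stake is the meaning of a descriptive figure. The SAP introduction says its analyses may go to competent authorities, presentations and manuscripts. A rate produced under 7.2 would carry a protocol-defined label without meeting the protocol's definition.

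**Working it through.** The plan gives no figure for assisted primary patency, so there is nothing to reproduce. The check applies both rules to the same subjects.

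**Step 1: case comparison.** Assume an in-window 12-month DUS with PSVR of 2.4 or less in every case.

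| History before the 12-month DUS | Protocol Table 25.2-1 | SAP 7.2 |
|---|---|---|
| No TLR | Patent | YES |
| Clinically-driven TLR for restenosis, no complete occlusion | Patent | YES |
| Clinically-driven TLR for complete occlusion | Not patent | YES |
| Bypass of the target lesion | Not patent | YES |

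The rules agree in the first two rows and disagree in the last two. As an illustration, take a lesion that occludes at month 5, is re-opened by clinically-driven TLR, and has a PSVR of 1.8 at month 12. It is YES under the SAP and not patent under the protocol.

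**Step 2: drop the scan assumption for bypass.** Footnote b waives follow-up DUS after target-lesion bypass. Without an in-window scan, SAP 7.2 cannot return YES. The fourth row therefore applies only to bypassed subjects who are scanned anyway. The third row has no such limit, because the waiver covers bypass only.

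**Step 3: does other SAP text restore the exclusion?**

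- SAP 5.8 keeps scans made after a TLR and leaves it to each endpoint definition to allow for the TLR. It spells out the consequence only for primary patency.
- SAP 7.1 makes that allowance. SAP 7.2, directly after it, does not.
- The conditional wording of 7.2 could be taken as a necessary condition to which others may be added. Its opening sentence rules that out by confining the derivation to one form, which shuts out the CEC and AE data.

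Nothing else in the SAP restores the exclusion.

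**Step 4: direction and size.** SAP 7.2 can give YES where the protocol gives not patent. No case in the table goes the other way, so the error can only raise the rate. With n subjects in the denominator, each misclassified subject raises it by 1/n. Protocol 11.1.1.2 supplies two reference sizes:

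- 60 enrolled in the primary cohort: 1/60 = 1.7 points.
- 50 evaluable at 30 days: 1/50 = 2.0 points.

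Neither document plans a 12-month denominator; a smaller one would make each step larger. The documents do not give the expected number of re-opened occlusions or scanned bypasses, so no total can be computed.

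**The case against.** The strongest reply is that the measure hardly matters. Assisted primary patency is not among the additional endpoints in Protocol 6.2.2. It is also absent from the secondary assessments in SAP 5.1 and from that section's content lists for the 30-day and 12-month reports. It appears only in a definitions table and a programming note, and even the listed additional assessments are observational. This stands, and it sets the grade of the point. It does not remove the point, because the protocol defines the measure and the SAP gives the programmers a rule that departs from the definition.

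A second reply is that the remedy may need data not shown to exist. The TLR definition in Table 25.2-1 turns on stenosis above 50% with recurrent ischemia, and neither document shows a CEC field for complete occlusion. SAP 5.7 sends re-intervention angiograms to the core laboratory, but Protocol 12.3 names only baseline angiograms and the 6- and 12-month DUS. This also stands, and the fix includes a check.

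A reader might infer three stronger things that the documents do not support:

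- **That every bypassed subject is counted as patent.** Footnote b means many may have no scan, and then 7.2 cannot return YES.
- **That the bias can be sized from Pathway PVD.** The protocol reports: "Primary and secondary duplex-documented patency rates at 12 months were 61.8% (76/123 lesions) and 81.3% (100/123 lesions), respectively". The gap is 100/123 − 76/123 = 24/123 = 19.5 points. Assuming that 10% to 50% of it came from re-opened occlusions would give about 2 to 10 points, but that fraction has no source. Nor is 19.5 points a ceiling here. Pathway PVD used a first-generation device, admitted tibial and peroneal lesions and Rutherford 1 to 5, and counted lesions. This trial takes one SFA/PPA target lesion per subject, in Rutherford 2 to 4.
- **That the trial's conclusion is at risk.** Neither primary endpoint uses patency.

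**Conclusion.** The contradiction is between current texts and is real. As written, SAP 7.2 counts as assisted-primary patent a lesion re-opened by clinically-driven TLR for complete occlusion, provided the in-window PSVR is 2.4 or less. It does the same for a bypassed subject only where an in-window scan exists.

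The per-subject effect assumes a denominator of 50 to 60; the total effect is unknown. Primary safety, primary effectiveness, study success and primary patency under SAP 7.1 are unaffected. Severity is minor: a derivation to correct before the measure is programmed or reported.

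**What to change.** Amend SAP 7.2 to keep the in-window DUS and PSVR condition and to return NO if either of the following occurred before the 12-month DUS, or by the end of the 12-month window (day 395 in SAP 5.8) when no DUS is done:

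- a CEC-adjudicated clinically-driven TLR for complete occlusion of the target lesion;
- a bypass of the target lesion, read from the AE form as in SAP 7.1.

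The end-of-window date is needed because bypassed subjects may have no scan to serve as a reference.

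Before finalising, confirm that occlusion status at TLR can be obtained from the CEC form or from the core-lab angiograms described in SAP 5.7. If the PSVR-only figure is kept, report it under a different label with its own definition. Table 25.2-1 has no entry for secondary patency, so that name would need defining first.

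The cost is a SAP amendment before analysis, which SAP 5.16 provides for, a short programming change using CEC and AE data that SAP 7.1 already reads, and the check on occlusion status. If that status is not recorded, it would have to be collected or read from the angiograms. The reported rate may be slightly less favourable.
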